## **10 Human Subjects Protections**

Each study participant or a LAR must sign and date an informed consent form. Approval of the Vanderbilt Institutional Review Board will be required before any participant is entered into the study.

### **10.1 Selection of Subjects**

Federal regulations at 45 CFR 46(a)(3) require the equitable selection of participants. Every adult patient for whom V-V ECMO is initiated at Vanderbilt University Medical Center or accepted on V-V ECMO from an outside institution will be screened to determine if the patient meets inclusion and exclusion criteria. Data that have been collected as part of routine clinical care will be reviewed to determine eligibility. If any patient meets criteria for study enrollment, then the attending physician responsible for his or her care will be asked for permission to approach the patient or his or her LAR for informed consent. Study exclusion criteria neither unjustly exclude classes of individuals from participation in the research nor unjustly include classes of individuals for participation in the research. Hence, the recruitment of participants conforms to the principle of distributive justice.

### **10.2 Justification of Including Vulnerable Subjects**

The present research aims to investigate the feasibility of a large multicenter trial evaluating the safety and efficacy of treating patients receiving V-V ECMO with low intensity anticoagulation. Patients receiving V-V ECMO have severe respiratory failure and are at high risk for mortality. Due to the nature of this patient population, many of these patients will have impaired decision-making capabilities. Therefore, this study would be virtually impossible to perform if only those participants with retained decision-making capacity were enrolled and would not be generalizable to the population of patients receiving venovenous ECMO. Hence, participants recruited for this trial are not being unfairly burdened with involvement in this research.

### **10.3 Informed Consent**

Federal regulations 45 CFR 46.111(a)(5) require that informed consent will be sought from each patient or the patient's LAR. Study personnel obtaining informed consent are responsible for ensuring that the patient or LAR understands the risks and benefits of participating in the study, answering any questions the patient or LAR may have throughout the study and sharing any new information in a timely manner that may be relevant to the patient's or LAR's willingness to permit the patient's continued participation in the trial. The study personnel obtaining informed consent will make every effort to minimize coercion. Whenever possible, consent will be obtained by a study team member separate from the person who obtained consent for cannulation and initiation of ECMO. All patients or their LARs will be informed of the objectives of the study and the potential risks. The informed consent document will be used to explain the risks and benefits of study participation to the patient or LAR in simple terms and to confirm that the patient or LAR is satisfied with his or her understanding of the risks and benefits of participating in the study and desires to participate in the study before the patient is entered into the study. The investigator is responsible for ensuring that informed consent is given by each patient or LAR. This includes obtaining the appropriate signatures and dates on the informed consent document prior to the performance of any protocol procedures including initiation of study intervention. If the potential participant is under the care of another physician (not the Investigator), the patient's physician will approach the patient first and obtain permission from the patient to be approached by the Investigator regarding the research opportunity.

### **10.4 Continuing Consent**

Patients for whom consent was initially obtained from a LAR, but who subsequently regain decision-making capacity while in hospital will be approached for consent for continuing participation, including continuance of data acquisition. The consent form signed by the LAR should reflect that such consent should be obtained.

### **10.5 Withdrawal of Consent**

Participating patients may withdraw or be withdrawn (by the LAR, treating physician, or investigator) from the trial at any time without prejudice. Data recorded up to the point of withdrawal will be included in the trial analysis, unless consent to use data has also been withdrawn. Withdrawal of consent prior to receipt of the study intervention will constitute a screen-failure and will be recorded. Withdrawal of consent after randomization and initiation of the study intervention will lead to discontinuation of study interventions, but site staff will request access to medical records for data related to the trial.

### **10.6 Identification of Legally Authorized Representatives**

Many of the patients approached for participation in this research protocol will have impaired decision-making capacity due to critical illness and will not be able to provide informed consent. Accordingly, informed consent will be sought from the patient's LAR.

Regarding consent from the LAR, the existing federal research regulations ('the Common Rule') states at 45 CFR 46.116 that "no investigator may involve a human being as a subject in research...unless the investigator has obtained the legally effective informed consent of the subject or the subject's legally authorized representative"; and defines at 45 CFR 46.102 (c) a LAR as "an individual or judicial or other body authorized under applicable law to consent on behalf of a prospective subject to the subject's participation in the procedures(s) involved in the research." The Office of Human Research Protections (OHRP) defined examples of "applicable law" as being state statutes, regulations, case law, or formal opinion of a State Attorney General that addresses the issue of surrogate consent to medical procedures. Such "applicable law" could then be considered as empowering the LAR to provide consent for participant participation in the research. Interpretation of "applicable law" may be state specific and will be addressed by the IRB.

According to a previous President's Bioethics Committee (National Bioethics Advisory Committee (NBAC)), an investigator should accept a relative or friend of the potential participant who is recognized as an LAR for purposes of clinical decision making under the law of the state where the research takes place. Finally, OHRP has stated in their determination letters that a surrogate could serve as a LAR for research decision making if such an individual is authorized under applicable state law to provide consent for the "procedures" involved in the research study.

## **10.7 Justification of Surrogate Consent**

According to the Belmont Report, respect for persons incorporates at least two ethical convictions; first, that individuals should be treated as autonomous agents, and second, that persons with diminished autonomy are entitled to protection. One method that serves to protect patients is restrictions on the participation of patients in research that presents greater than minimal risk.

Commentators and research ethics commissions have held the view that it is permissible to include incapable participants in greater than minimal risk research as long as there is the potential for beneficial effects and that the research presents a balance of risks and expected direct benefits similar to that available in the clinical setting. Several U.S. task forces have deemed it permissible to include incapable participants in research. For example, the American College of Physicians' document allows surrogates to consent to research involving incapable participants only "if the net additional risks of participation are not substantially greater than the risks of standard treatment". Finally, NBAC stated that an IRB may approve a protocol that presents greater than minimal risk but offers the prospect of direct medical benefits to the participant, provided that "the potential subject's LAR gives permission...".

Consistent with the above ethical sensibilities regarding the participation of decisionally incapable participants in research and the previous assessment of risks and benefits in the previous section, the present trial presents a balance of risks and potential direct benefits that is similar to that available in the clinical setting.

## **10.8 Confidentiality**

Federal regulations at 45 CFR 46 111 (a) (7) requires that when appropriate, there are adequate provisions to protect the privacy of participants and to maintain the confidentiality of data. At no time during the course of this study, its analysis, or its publication will patient identities be revealed in any manner. The minimum necessary data containing patient or provider identities will be collected. All patients will be assigned a unique study ID number for tracking. All data collected for this study will be entered directly into a secure online database. All data will be maintained in the secure online database until the time of study publication. At the time of publication, a de-identified version of the database will be generated.

## 11 Adverse Events

Assuring patient safety is an essential component of this protocol. Both anticoagulation strategies have been used for decades in critically ill patients with an established safety profile. Treatment with low intensity anticoagulation for patients receiving V-V ECMO, however, raises unique safety considerations. This protocol addresses these considerations through:

1. Exclusion of patients with active bleeding and patients assessed as at high risk of bleeding (for whom the moderate intensity anticoagulation strategy might be unsafe);
2. Exclusion of patients with active thromboembolism or patients felt to be at high risk of thromboembolism (for whom the low intensity anticoagulation strategy might be insufficient);
3. Proactive education of treating clinicians regarding signs of oxygenator inefficiency and failure and ECMO circuit component thrombosis;
4. On-study monitoring of circuit components for signs of thrombosis and oxygenator insufficiency/failure;
5. Systematic collection of safety outcomes relevant to anticoagulation strategy during V-V ECMO;
6. Structured reporting of adverse events

### 11.1 Adverse Event Definitions

**Adverse Event:** Any untoward medical occurrence associated with the use of a drug or a study procedure, whether or not considered drug related.

**Serious Adverse Event:** A serious adverse event is any adverse event that results in one of the outcomes listed in section 11.3 below.

**Adverse Reaction:** An adverse reaction means any adverse event caused by a study intervention. An adverse reaction is a subset of all suspected adverse events where there is a reason to conclude that the study intervention caused the event.

**Suspected Adverse Reaction:** Any adverse event for which there is a reasonable possibility that the study procedures caused the adverse event. Reasonable possibility means there is evidence to suggest a causal relationship between the study procedures and the adverse event. A suspected adverse reaction implies a lesser degree of certainty about causality than adverse reaction.

**Suspected Unexpected Serious Adverse Reaction (SUSAR):** An adverse reaction that is both unexpected (not consistent with risks outlined in the study protocol or investigator brochure), serious, and meets the definition of a suspected adverse reaction.

### 11.2 Safety Monitoring

Assuring patient safety is an essential component of this protocol. Site investigators have primary responsibility for the safety of the individual patients enrolled at their respective institutions. Each investigator has primary responsibility for the safety of the individual participants under his or her care. The Investigators will evaluate patients for protocol adherence and adverse events daily from **enrollment through 24 hours after the end of the intervention period** (the first of diagnosis of a major bleeding event, diagnosis of a thrombotic event, placement of an arterial ECMO cannula, decannulation from ECMO, or death). If adverse events are identified, site investigators will determine if such adverse events are reportable. Thereafter, adverse events are not required to be reported unless the investigator feels the adverse event was definitely or possibly related to study intervention or procedures. Serious adverse events that are definitely or probably related to study procedures will be considered reportable and thus collected in the adverse events case reports forms. Investigators will be asked to grade the strength of the relationship of an adverse event to study drug or study procedures as follows:

- Definitely Related: The event follows: a) A reasonable, temporal sequence from a study procedure; and b) Cannot be explained by the known characteristics of the patient's clinical state or other therapies; and c) Evaluation of the patient's clinical state indicates to the investigator that the experience is definitely related to study procedures.
- Probably Related: The event should be assessed following the same criteria for "Definitely Associated". If in the investigator's opinion at least one or more of the criteria are not present, then "probably" associated should be selected.
- Probably Not Related: The event occurred while the patient was on the study but can reasonably be explained by the known characteristics of the patient's clinical state or other therapies.
- Definitely Not Related: The event is definitely produced by the patient's clinical state or by other modes of therapy administered to the patient.
- Uncertain Relationship: The event does not meet any of the criteria previously outlined.

Serious adverse events that are definitely or probably related to study procedures will be collected from randomization until death or discharge.

### 11.3 Serious Adverse Events

Serious adverse event collection begins after randomization and study procedures have been initiated. If a patient experiences a serious adverse event after consent, but prior to randomization or starting study procedures, the event will NOT be collected.

As per the FDA and NIH definitions, a serious adverse event is any adverse event that results in one of the following outcomes:

- Death
- A life-threatening experience (that is, immediate risk of dying)
- Prolonged inpatient hospitalization or re-hospitalization
- Persistent or significant disability/incapacity

Reportable serious adverse events that may not result in death, be life-threatening, or require hospitalization may be considered serious adverse events when, based upon appropriate medical judgment, they may jeopardize the patient and may require medical or surgical intervention to prevent one of the outcomes listed in this definition.

**Clinical Outcomes.** In this study of critically ill patients at high risk for death and other adverse outcomes due to their underlying critical illness, clinical outcomes, including death and organ dysfunction, will be systematically collected and analyzed for all patients. Death and organ dysfunction will be reported as outcomes and not as AEs unless the treating clinician or study personnel believe the event is related or potentially related to the study OR is more severe or prolonged than expected. This approach—considering death and organ dysfunction as outcomes rather than AEs and systematically collecting these outcomes for analysis—is common in ICU trials. This approach ensures comprehensive data on death and organ dysfunction for all patients, rather than relying on sporadic AE reporting to identify these important events. The following is a list of items that will be systematically collected as primary or secondary clinical outcomes. These will not be reported as AEs during this study, unless determined by treating clinicians or study personnel to be related or potentially related to the study or more severe or prolonged than expected:

1. Death (all deaths occurring prior to hospital discharge will be reported on the eCRF in the vital status at hospital discharge section)
2. Major or minor bleeding
3. Thromboembolic event
4. Cannula-associated DVT
5. Hemolysis
6. Thrombocytopenia
7. Heparin-induced thrombocytopenia
8. ECMO circuit or circuit component thrombosis
9. Renal Failure
10. Duration of ECMO support, ECMO recannulation
11. Duration of ICU admission, ICU readmission
12. Duration of hospitalization, hospital readmission

**Communication and Reporting of Adverse Events.** In order to ensure proper and timely reporting of reportable adverse events, there will be a clear communication plan for all study personnel to follow. Site investigators must alert the principal investigator of any **serious adverse event that is definitely or possibly related to study procedures** within 24 hours of investigator awareness of the event. Alerts issued via telephone are to be immediately followed with official notification on the adverse event case report form. The principal investigator or a delegate will report all unexpected deaths, serious adverse events that are definitely or probably related, and SUSARs to the IRB within 7 calendar days of the Investigator's knowledge of the event.

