#### **Assessments between Randomization and Hospital Discharge**

- Date and time of all major bleeding events from randomization to hospital discharge
- Date and time of all thromboembolic events from randomization to hospital discharge
- Anticoagulation strategy at 7 AM each day from randomization to the first of: diagnosis of a major bleeding event, diagnosis of a thrombotic event, placement of an arterial ECMO cannula, decannulation from ECMO, or death; indication for receiving anticoagulation strategy other than intervention strategy
- Randomized assignment to low intensity or moderate intensity anticoagulation strategy
- Number of hours during the intervention period receiving moderate intensity anticoagulation
- Number of hours during the intervention period receiving low intensity anticoagulation
- Date, time, and value of all PTTs and all Anti-XA laboratory results from randomization to 24 hours following decannulation
- Date, time, and type of all major bleeding events from randomization to hospital discharge
- Date, time, and type of all thromboembolic events from randomization hospital discharge
- ECMO blood flow rate, daily during the intervention period
- ECMO fraction of delivered oxygen, daily during the intervention period
- Transmembrane pressures, daily during the intervention period
- Receipt of continuous renal replacement therapy, daily during the intervention period
- Receipt of anticoagulation for continuous renal replacement therapy patency (drug, dose, route of administration), assessed daily during the intervention period
- Volume of packed red blood cells transfused from randomization to 24 hours following decannulation
- Volume of platelets transfused from randomization to 24 hours following decannulation
- Volume of fresh frozen plasma transfused from randomization to 24 hours following decannulation
- Volume of cryoprecipitate transfused from randomization to 24 hours following decannulation
- Lowest documented ECMO blood flow rate during the intervention period
- Date and time of each circuit exchange
- Date and time of each circuit component exchange
- Indication for circuit and circuit component exchanges
- Post-decannulation DVT
- Lowest hemoglobin from randomization to 24 after decannulation
- Lowest documented platelet count from randomization to 24 hours after decannulation
- Highest total and indirect bilirubin values from randomization to 24 hours after decannulation

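### Section 11.3 exempts minor bleeding, ECMO recannulation and ICU readmission from adverse-event reporting as collected outcomes, but 7.1 has no field for them; the form and alert thresholds also disagree

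*Combined protocol and SAP*

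**What the plan says.** Section 11.3 lists twelve entries, introduced by "The following is a list of items that will be systematically collected as primary or secondary clinical outcomes". They are not reported as adverse events "unless determined by treating clinicians or study personnel to be related or potentially related to the study or more severe or prolonged than expected". The argument for this approach, made there for death and organ dysfunction, is that it gives complete data on every patient "rather than relying on sporadic AE reporting to identify these important events".

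Four entries matter here: "Major or minor bleeding" (entry 2), "Duration of ECMO support, ECMO recannulation" (entry 10), "Duration of ICU admission, ICU readmission" (entry 11) and "Duration of hospitalization, hospital readmission" (entry 12).

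The bleeding field in 7.1 reads "Date, time, and type of all major bleeding events from randomization to hospital discharge". For ECMO and ICU course after randomization, 7.1 has a decannulation date and time and an ICU discharge date. Section 7.2.4 lists bleeding events per ECMO day and up to death or discharge, with no grade attached. Section 14 ends follow-up at hospital discharge.

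Section 11.2 gives a five-grade relatedness scale: *Definitely Related*, *Probably Related*, *Probably Not Related*, *Definitely Not Related* and *Uncertain Relationship*. The reporting rules that rely on it are spread over 11.2 and 11.3.

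**The concern.** Exempting expected events from adverse-event reporting is sound when those events are captured elsewhere for every patient. If an exempt event has no field, the exemption removes its only routine record, and what remains is the case-by-case reporting that 11.3 sets out to avoid. The protocol's secondary aim is to define and measure outcomes for the later trial, and non-major bleeding is an obvious candidate in a comparison of anticoagulation intensity. The trial is open label, so capture that depends on clinicians' judgement could differ between arms.

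The threshold problem is separate. If the rules for one form use different words, and one of those words is not on the scale, the same serious event may go on the form at one of the three sites listed in 5.1 and not at another.

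**Working it through.** No arithmetic applies beyond counting; the check sets the sections side by side.

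**Step 1. Exempt events against 7.1 and 7.2**

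| Event in the 11.3 list | Field in 7.1 | Named in 7.2 |
|---|---|---|
| Minor bleeding | None; the bleeding fields are for major events | No; 7.2.4 has ungraded bleeding events |
| ECMO recannulation | None | No |
| ICU readmission | None | No |
| Hospital readmission | None; beyond follow-up (section 14) | No |

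Where an event can recur, 7.1 usually says so: it asks for *all* major bleeding events and *each* circuit exchange. The decannulation and ICU discharge dates carry no such word, and 7.1 does not say whether they are first or final. A return to ECMO or to the ICU may therefore not be identifiable. ECMO-free and ICU-free days in 7.2.4 have no stated handling of a return either.

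**Step 2. Do other routes fill the gap?**

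- *Adverse-event route.* The exemption lifts for events judged related, potentially related, or more severe or prolonged than expected. Events judged unrelated and as expected stay exempt. Daily evaluation under 11.2 stops 24 hours after the intervention period. Decannulation ends that period if nothing else has, so a recannulation more than 24 hours later falls outside it.
- *Reason for changing strategy.* 7.1 records why a patient is off the assigned strategy, and 6.1.3 lists non-major bleeding as a permitted reason. This captures a bleed only if the strategy changed, and only during the intervention period.
- *Laboratory and transfusion data.* Lowest hemoglobin and red-cell volume are objective but do not identify a bleeding event.

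**Step 3. Reporting thresholds**

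| Rule | Section | Relatedness required |
|---|---|---|
| Serious events on the adverse event form | 11.2 | definitely or probably |
| Serious events collected to death or discharge | 11.2 | definitely or probably |
| Report of serious events to the IRB | 11.3 | definitely or probably |
| Any adverse event after daily evaluation ends | 11.2 | definitely or possibly |
| 24-hour alert for serious events, then the form if by telephone | 11.3 | definitely or possibly |

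The first three rules name two grades and so exclude *Uncertain*. The last two use a word that is not a grade, so it is unclear whether *Uncertain* is included. The fourth rule covers late adverse events of any seriousness, so its scope differs. The direct conflict is between the first and the fifth: if *possibly* takes in *Uncertain*, a telephone alert puts on the form an event that the 11.2 form rule leaves off.

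**Step 4. Overlap of two grades**

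*Definitely Related* needs three criteria. Criterion b is that the patient's condition or other treatment cannot explain the event. *Probably Related* applies when one or more criteria are missing. *Probably Not Related* applies when the patient's condition or other treatment can reasonably explain the event. An event with such a reasonable explanation fails b. As worded, it therefore fits *Probably Related* (reportable if serious) and also *Probably Not Related* (not reportable under the form rule).

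**The case against.** Much of the case on the other side stands, and it limits the point.

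- A reader might infer that all exempt events go unreported. They do not: the exemption is conditional, and daily evaluation covers the intervention period plus 24 hours. Only events judged unrelated and as expected are lost.
- A reader might infer that the rest of the 11.3 list is fully covered. Some of it rests on proxies: hemolysis on LDH and bilirubin, renal failure on renal replacement therapy, circuit thrombosis on exchanges and their indications. The three named events are those with no field at all, not a precise coverage rate.
- Minor bleeding may already be intended as an outcome. Section 7.2.4 leaves bleeding events ungraded but specifies major bleeding for attributable death. If so, 7.2.4 asks for something 7.1 does not collect; the field is still missing.
- A wider alert to the principal investigator than to the IRB is legitimate. The fault is that its width is given in a word outside the scale and tied to the same form.
- A reader might infer that every event failing criterion b falls into both grades. It does not: an explanation may be conceivable without being reasonable, so the overlap covers only events with a reasonable one.
- Read literally, *Uncertain* would never be used, because any event missing a criterion already counts as *Probably Related*. Its place in the alert rule matters only if investigators use the grade, as its presence on the scale suggests.
- Different capture by arm is a possibility that the documents do not demonstrate, in a descriptive pilot with no inferential tests.

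**Conclusion.** The point holds. Three exempt events have no field in 7.1 and are not named in 7.2, and a fourth cannot occur within follow-up. The form rule in 11.2 and the alert rule in 11.3 differ for the same form, and two grades overlap for events with a reasonable alternative explanation. These are rules that misfire when followed as written, so they should be corrected rather than left to site practice.

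The size is modest. The documents give no rate for the three events, so the number missed cannot be computed; enrolment is capped at 30 patients. A reader might infer that the primary comparison is compromised. The documents do not support that: major bleeding, thromboembolism and death are recorded whatever the relatedness grade.

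The conclusion assumes that 7.1 is the full list of recorded variables, as it presents itself. The case report form could hold further fields, but nothing in the documents says so.

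**What to change.** 1. In 7.1, add fields for clinically overt non-major bleeding, ECMO recannulation and ICU readmission.
2. In 7.2.4, state whether bleeding events means major bleeding only.
3. In 11.3, delete hospital readmission from the exempt list.
4. In 11.2 and 11.3, restate the form and alert thresholds in the scale's own grades and say whether *Uncertain* triggers an alert. An alert wider than the IRB report may stay if that is stated.
5. Redefine *Probably Related* and *Probably Not Related* so that no event fits both.

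Taking the three events off the 11.3 list instead would not capture them, because an unrelated event meets neither the 11.2 form rule nor the 11.3 alert rule.

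The cost is up to three chart-review fields for at most 30 patients, some redrafting, and somewhat more event reports.
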